#### PHARMACODYNAMICS

-			
14.2.3.1	Descriptive Statistics of Actual Values, Changes from Baseline, Changes from 1904 Baseline and Changes from Treatment Period Baseline in Total IgG Level and IgG Subtype Levels by Visit	ROLL	
14.2.3.2	Descriptive Statistics of Actual Values, Percent Changes from Baseline, Percent Changes from 1904 Baseline and Percent Changes from Treatment Period Baseline in Total IgG Level and IgG Subtype Levels by Visit	ROLL	
14.2.3.3	Descriptive Statistics of Actual Values, Changes from Baseline, Changes from 1904 Baseline and Changes from Treatment Period Baseline in anti-Dsg-1/-3 antibodies by Visit	ROLL	
14.2.3.4	Descriptive Statistics of Actual Values, Percent Changes from Baseline, Percent Changes from 1904 Baseline and Percent Changes from Treatment Period Baseline in anti-Dsg-1/-3 antibodies by Visit	ROLL	TL
IMMMUNO	OGENICITY		
14.2.4.1	ADA: Anti-Drug Antibodies to Efgartigimod Sample Classification by Analysis Visit by Overall Anti-Drug Antibodies Participant Classification	SAF	
14.2.4.2	ADA: Anti-Drug Antibodies to Efgartigimod Participant Classification, Prevalence and Incidence	SAF	
14.2.4.3	NAb: Neutralizing Antibodies to Efgartigimod Sample Classification by Analysis Visit by Overall Neutralizing Antibodies Participant Classification	SAF	
14.2.4.4	NAb: Neutralizing Antibodies to Efgartigimod Participant Classification, Prevalence and Incidence	SAF	
14.2.4.5	NAb: Neutralizing Antibodies Positives to Efgartigimod Sample Classification by Overall Efgartigimod Anti-Drug Antibodies Participant Classification	SAF	
14.2.4.6	ADA: Descriptive Statistics of ADA Against Efgartigimod Titer Values by ADA Participant Classification Against Efgartigimod	SAF	
SAFETY			
ADVERSE	EVENTS		
14.3.1.1.1	Adverse Events Overview	SAF - ROLL	TL
14.3.1.1.2	Adverse Events Overview by Disease Status at Roll-over	SAF - ROLL	TL
14.3.1.2.1	Treatment-Emergent and Post-Treatment Adverse Events by MedDRA System Organ Class and Preferred Term	SAF - ROLL	TL
14.3.1.2.2	Treatment-Emergent and Post-Treatment Adverse Events by MedDRA System Organ Class and Preferred Term by Disease Status at Roll-over	SAF - ROLL	TL
14.3.1.2.3	Most Common (>=5% in the Total Group) Treatment-Emergent Adverse Events by MedDRA System Organ Class and Preferred Term	SAF	TL
14.3.1.3	Treatment Related Treatment-Emergent Adverse Events by MedDRA System Organ Class and Preferred Term	SAF	
	Page 62 of 84		

Page 62 of 84

System Version: 1.0, Status: Approved, Document ID: VV-TMF-172580

_	SGS	Statistical Analysis Plan	
Al	RGX-113-1905	Final analysis	Final 1.0 of 26APR2024
•			

14.3.1.4.1	4.3.1.4.1 Serious Treatment-Emergent Adverse Events by MedDRA System Organ Class and Preferred Term		TL
14.3.1.4.2	Serious Treatment-Emergent Adverse Events by MedDRA System Organ Class and Preferred Term by Disease Status at Roll-over	SAF	TL
14.3.1.5	Serious Treatment Related Treatment-Emergent Adverse Events by MedDRA System Organ Class and Preferred Term	SAF	
14.3.1.6	Serious Prednisone Related Treatment-Emergent Adverse Events by MedDRA System Organ Class and Preferred Term	SAF	
14.3.1.7.1	Grade 3 or More Treatment-Emergent Adverse Events by MedDRA System Organ Class and Preferred Term	SAF	TL
14.3.1.7.2	Grade 3 or More Treatment-Emergent Adverse Events by MedDRA System Organ Class and Preferred Term by Disease Status at Roll- over	SAF	TL
14.3.1.8	Treatment Related Grade 3 or More Treatment-Emergent Adverse Events by MedDRA System Organ Class and Preferred Term	SAF	
14.3.1.9	Prednisone Related Treatment-Emergent Adverse Events by	SAF	

MedDRA System Organ Class and Preferred Term 14.3.1.10 Procedures Related Treatment-Emergent Adverse Events by SAF MedDRA System Organ Class and Preferred Term Treatment-Emergent Adverse Events Leading to Discontinuation of SAF 14.3.1.11.1 TL IMP by MedDRA System Organ Class and Preferred Term 14.3.1.11.2 Treatment-Emergent Adverse Events Leading to Discontinuation of TL SAF IMP by MedDRA System Organ Class and Preferred Term by Disease Status at Roll-over 14.3.1.12.1 Treatment-Emergent Adverse Events of Special Interest by SAF TL MedDRA System Organ Class and Preferred Term Treatment-Emergent Adverse Events of Special Interest by SAF 14.3.1.12.2 TL MedDRA System Organ Class and Preferred Term by Disease

	Status at Roll-over				
14.3.1.13	Treatment Related Treatment-Emergent Adverse Events of Special Interest by MedDRA System Organ Class and Preferred Term	SAF			
14.3.1.14	Treatment-Emergent Injection-Related Reactions by MedDRA System Organ Class and Preferred Term	SAF			
14.3.1.15	Serious Treatment-Emergent Injection-Related Reactions by MedDRA System Organ Class and Preferred Term	SAF			
14.3.1.16.1	Treatment-Emergent Injection Site Reactions - Overview	SAF	TL		
14.3.1.16.2	Treatment-Emergent Injection Site Reactions – Overview by Disease Status at Roll-over	SAF	TL		
14.3.1.16.3	Treatment-Emergent Injection Site Reactions by MedDRA System Organ Class and Preferred Term	SAF	TL		
14.3.1.16.4	Treatment-Emergent Injection Site Reactions by MedDRA System Organ Class and Preferred Term by Disease Status at Roll-over	SAF	TL		
LABORAT	LABORATORY DATA				

14.3.2.1 Descriptive Statistics of Laboratory Test Actual Values and SAF Changes from Baseline

SGS	Statistical Analysis Plan			
ARGX-113-190	95 Final analysis	Fir	nal 1.0 of 26	APR2024
14.3.2.2	Descriptive Statistics of Albumin and Low-Density Lipopro Cholesterol Actual Values and Changes from Baseline and Treatment Period Baseline	otein-	SAF	TL
14.3.2.3	Descriptive Statistics of Albumin and Low-Density Lipopro Cholesterol Actual Values and Percent Changes from Basel Treatment Period Baseline		SAF	TL
14.3.2.4	Cross-Tabulation of Laboratory Abnormalities Versus Baseline		SAF	
14.3.2.5	Cross-Tabulation of Laboratory Toxicity Grades Versus Ba	seline	SAF	
VITAL SIG	NS			
14.3.3.1	Descriptive Statistics of Vital Signs Actual Values and Char from Baseline	ıges	SAF	
14.3.3.2	Cross-Tabulation of Vital Signs Abnormalities Versus Base	line	SAF	
ECG				
14.3.4.1	Descriptive Statistics of ECG Actual Values and Changes fr Baseline	om	SAF	
14.3.4.2	Cross-Tabulation of ECG Abnormalities Versus Baseline		SAF	
14.3.4.3 Cross-Tabulation of QTCB/QTCF Abnormalities Versus Baseline		iseline	SAF	
14.3.4.4	Tabulation of QTc Change Abnormalities		SAF	

#### 8.2 LISTINGS

#### GENERAL CHARACTERISTICS

[figure not shown]
16.2.1.1	Analysis Sets and Disease Status at Roll-over	ROLL				
16.2.1.2	Study Visits	ROLL				
16.2.1.3	Study and Treatment Discontinuation	ROLL				
16.2.2.1	Protocol Deviations	ROLL				
16.2.2.2	Violations on Eligibility Criteria	ROLL				
16.2.2.3	Covid-19 Related Comments	ROLL				
16.2.4.1	Demographic Data	ROLL				
16.2.4.2	Baseline Disease Characteristics	ROLL				
16.2.4.3	Prior and Concomitant Therapies	ROLL				
16.2.4.4	Prior and Concomitant Procedures	ROLL				
16.2.5.1	IMP Administration	SAF				
16.2.5.2	Prednisone Administration and cumulative dose	ROLL				
16.2.5.3	NCPD and cumulative dose until endpoints	ROLL				
16.2.5.4	IMP (Self-)Administration Training	SAF				
PHARMA	COKINETICS					
16.2.5.5	Individual Efgartigimod Serum Concentrations and Actual Blood Sampling Times	SAF				
EFFICACY	EFFICACY					
16.2.6.1	Disease Status and Flares	ROLL				
16.2.6.2	Disease Status: Derived Parameters	ROLL				
	Page 64 of 84					

CONFIDENTIAL AND PROPRIETARY

System Version: 1.0, Status: Approved, Document ID: VV-TMF-172580

SG	S Statistical Analysis Plan	
ARGX-113-1	905 Final analysis	Final 1.0 of 26APR2024
16.2.6.3	Lesion Assessment	ROLL
16.2.6.4	PDAI	ROLL
16.2.6.5	ABQOL	ROLL
16.2.6.6	EQ-5D-5L	ROLL
16.2.6.7	C-GTI	ROLL
16.2.6.8	GTI specific list	ROLL
PHARMA	CODYNAMICS	
16.2.6.9	Total IgG and IgG Subtypes	ROLL
16.2.6.10	Anti-Dsg-1/-3 antibodies	ROLL
IMMUNO	GENICITY	
16.2.6.11	Efgartigimod Anti-drug Antibodies and Neutralizing Antibodies	SAF
SAFETY		
ADVERSI	E EVENTS	
16.2.7.1	Adverse Events	SAF
16.2.7.2	Serious Adverse Events	SAF
16.2.7.3	Fatal Adverse Events	SAF
16.2.7.4	Treatment-Emergent Adverse Events Leading to Discontinuation o IMP	f SAF
16.2.7.5	Adverse Events of Special Interest	SAF
16.2.7.6	Adverse Events: Coding Information	ROLL
LABORA	TORY DATA	
16.2.8.1	Laboratory Test Results for Participants with Abnormal Values	SAF
VITAL SI	GNS	
16.2.9.1	Vital Signs Results for Participants with Abnormal Values	SAF
ECG		
16.2.10.1	ECG Results for Participants with Abnormal Values	SAF
PHYSICA	L EXAMINATION	
16.2.11.1	Physical Examination Abnormalities	SAF

Document template OTH.STAT.010 v3

## 9. APPENDICES

#### 9.1 GTI: DERIVATION OF CWS AND AIS

#### 9.1.1 Allocate weights

Weights per item are attributed as specified below. GTI at Wx is evaluated versus previous GTI assessment. The first time point is referred to as *start (or previous)* and the second time point within each comparison is referred to as *follow-up (or current)*.

Increase, decrease or no change in medication intake compared to previous assessment are checked in the GTI assessment. A missing evaluation, including for external data, will be considered as no change with weight=0.

External GTI data (i.e. LDL/HbA1c/BP and BMI) are allocated to a GTI assessment based on dates. The last available value of these external data since previous GTI assessment will be used.

Changes from severe to moderate do not have any impact on calculation of CWS/AIS. Severe outcome on an item however is captured on the specific list (SL).

SGS	Statistical Analysis Plan	
ARGX-113-1905	Final analysis	Final 1.0 of 26APR2024

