- ^k Clinical blood laboratory tests will include hematology and blood chemistry at all visits. The hematology profile includes hemoglobin, hematocrit, MCV, RBC count, platelet count, and WBC count with differential. The blood chemistry profile includes sodium, potassium, calcium, HbA1c, creatinine, creatinine clearance, BUN, ALT, AST, total bilirubin, GGT, CRP, ALP, LDH, LDL-C, uric acid, total protein, and albumin.
- ¹ PK and PD (total IgG and IgG subtypes) samples will be taken every 4 weeks as long as the participant is receiving efgartigimod PH20 SC treatment (until CRmin or the next on-site visit) and 4 weeks after CRmin (or the next on-site visit; this also applies if the participant achieved CRmin in ARGX-113-1904) or EoT. Blood samples will be taken predose (within 2 hours before the start of IMP administration during visits when IMP is administered).
- ^m At unscheduled visits, blood samples for PK will only be taken if IMP is administered.
- ⁿ Blood samples will be taken to test for immunogenicity to efgartigimod in serum and rHuPH20 in plasma every 4 weeks while the participant is receiving efgartigimod PH20 SC treatment (until CRmin or the next on-site visit) and 4 and 8 weeks after CRmin (or the next 2 on-site visits; this also applies if the participant achieved CRmin in ARGX-113-1904) or EoT. NAb will be tested for all confirmed positive immunogenicity samples.
- ° Questionnaires are to be completed before any other assessment.
- ^p Disease assessment parameters include DC, EoC, CR, CRmin, CRoff, flare, and treatment failure. Participants who have achieved CR and have new lesions should come to the clinic for an unscheduled visit for disease assessment.
- ^q Samples for lymphocyte populations will be taken at selected sites only: optionally at on-site visits at W13 (±2 weeks), W26 (±2 weeks), W39 (±2 weeks), W52 (±2 weeks) or EoT/ET and EoS, and mandatory at on-site visits at W52 (±2 weeks) or EoT/ET and EoS for participants in CRmin or CRoff.
- ^r The GTI assessment will be performed at visit 1, W26 (or the next on-site visit), and W52.
- ^s Participants and/or their caregivers will be invited to receive at least 1 refresher training for self-administration, or caregiver-supported administration of IMP. Training will continue until deemed successfully completed by authorized staff.

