- The C-GTI, which serves as a primary instrument intended to capture common glucocorticoid toxicities (ie, toxicities that are likely due to glucocorticoid exposure and sensitive to cumulative doses over the period of 6 months to 3 years), has 9 functional domains (specifically: BMI, glucose control, blood pressure, lipid metabolism, bone mineral density, muscle strength, skin toxicity, neuropsychiatric effects, and infection). Each of the domains contains 3 to 4 weighted items that correspond to varying degrees of glucocorticoid toxicity within their respective domain. Among the 9 GTI domains, bone mineral density is excluded if the GTI will be measured at intervals shorter than 1 year, because bone densitometry is not sufficiently reliable in measuring changes at shorter intervals. Therefore, in the context of the ARGX-113-1904 trial with a maximum duration of 30 weeks, the index is truncated by removing the "bone mineral density" domain. Development of the GTI beyond the original validation work has suggested 2 approaches to analysis. These approaches provide complementary information about the ability of an investigational agent to reduce GC toxicity and also optimize the granularity with which the GTI captures the GC toxicity. The CWS is designed to assess cumulative GC toxicity, regardless of whether the toxicity has lasting effects or is transient. New toxicities that occur are added, but toxicities that appear to resolve on follow-up are not removed. Thus, the CWS serves as a lasting record of GC toxicity observed, and can only increase or remain the same over time. In the case of the presence of some GC toxicity at baseline, the AIS can be used to establish that a new therapy is effective at diminishing any baseline GC toxicity over time. With the AIS, toxicities can be removed if improvement occurs, and added if worsening occurs. If toxicities present at baseline or occurring during the trial resolve over the course of follow-up, then that improvement is reflected in a negative score for that item during the interval. Both the CWS and the AIS are calculated for each interval, and then the interval scores are summed.

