#### 4.1.3.6 OTHER EFFICACY ENDPOINTS

Descriptive statistics will be provided for the number of flares. Tables will be provided for PV participants and all participants (PV+PF), overall and by disease status at roll-over.

SGS	Statistical Analysis Plan	
ARGX-113-1905	Final analysis	Final 1.0 of 26APR2024

Frequency tabulations will be provided for the percentages of treatment failure (with 95% exact confidence interval) and its different reasons, overall and by disease status at roll-over.

PDAI activity subscores (mucosal, skin and scalp), PDAI activity score and PDAI total score will be summarized by means of descriptive statistics at each analysis visit. Actual values, changes from baseline and percent changes from baseline will be tabulated by analysis visits overall. Additionally, changes and percent changes versus 1904 baseline will be tabulated by analysis visits overall. Furthermore, actual values, changes from TPnB and percent changes from TPnB will be tabulated by analysis visits by period/subperiod. Tables to be provided for PV participants and for all participants (PV+PF).

Frequency tabulations will be provided for the percentages of participants within each outcome of QoL questionnaire items (ABQOL and EQ-5D-5L) at each analysis visit. Additionally, cumulative percentages (starting with the best outcome result) will be calculated. Descriptive statistics will be provided for the total ABQOL score and for the EQ-5D-5L VAS score.

Descriptive statistics will be provided for the C-GTI scores AIS and CWS. C-GTI will be analysed on complete cases: i.e. participants with C-GTI at baseline and at least one post-baseline visit. Participants where first post-baseline GTI improvements/worsening have not been obtained with respect to the baseline moment but with respect to a later moment (i.e. no GTI assessment at baseline visit) are excluded from analyses and are only listed.

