## 9.1.2 CWS and AIS calculation

## 9.1.2.1 CWS

The CWS is calculated as the sum of the worsening items: i.e. with weights >0. For the items with subitems, i.e. skin toxicity and neuropsychiatric effects, only the subitem with the highest positive weight is used. As an example, if neither insomnia nor depression were present at the start of the GTI interval but there is mild insomnia and moderate depression present at post-baseline, then only the moderate depression is used for the neuropsychiatric weight (+74 points).

In the CWS calculation, the most severe infection in every GTI interval is scored (so in case of 2 periods, the score for an infection is counted twice for the overall CWS at endpoint).

CWS is calculated at W26 and at W52 as the sum of the worsening items in all postbaseline timepoints up to that timepoint respectively. The overall CWS at endpoint is the sum of all worsening items over all post-baseline timepoints.

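### A GTI domain left blank at week 26 scores no change and, read literally, scores no change again at week 52, so a lasting worsening in BMI, myopathy, skin or neuropsychiatric effects can go unscored.

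*SAP*

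**What the plan says.** SAP 9.1.1 sets the comparator: "GTI at Wx is evaluated versus previous GTI assessment". It sets the missing-data rule in the same section: "A missing evaluation, including for external data, will be considered as no change with weight=0". For the external items (LDL, HbA1c, blood pressure, BMI) it adds: "The last available value of these external data since previous GTI assessment will be used".

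SAP 9.1.2.1 then defines the score: "The CWS is calculated as the sum of the worsening items: i.e. with weights >0", and "The overall CWS at endpoint is the sum of all worsening items over all post-baseline timepoints". The AIS in SAP 9.1.2.2 sums negative as well as positive weights.

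The schedule gives two intervals only. A footnote to Table 1 of the protocol's Schedule of Activities reads: "The GTI assessment will be performed at visit 1, W26 (or the next on-site visit), and W52". Table 2 has the same rule. Protocol 8.3.2 schedules weight at roll-over, week 26 (or the next on-site visit) and week 52, with a re-measurement if there has been an obvious change.

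On who is analysed, SAP 4.1.3.6 says "C-GTI will be analysed on complete cases", and the same sentence defines these as participants with a baseline and at least one post-baseline C-GTI.

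The SAP does not say what week 52 is compared with when a single domain has no week 26 value.

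**The concern.** The C-GTI is the endpoint for a stated secondary objective, the health impact of glucocorticoid use. Protocol 8.3.10 presents the CWS as a lasting record of toxicity that "can only increase or remain the same over time". A zero that stands for an unrecorded domain looks the same in that record as a zero that stands for observed absence of change.

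The two rules also compound. A blank at week 26 removes the end of the first interval and the start of the second, so one gap can cost both. The outcome is uneven as well. A participant who misses the whole week 26 GTI has roll-over as the previous assessment, so week 52 is scored against it. A participant who attends with one domain blank may lose that domain for the year.

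**Working it through.** **Inputs.** Weights from SAP 9.1.1, sums from SAP 9.1.2, assessments at roll-over, week 26 and week 52.

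**The plan's own figures first.**
- CWS example (insomnia none to mild, depression none to moderate): max(+11, +74) = +74, as the SAP states.
- AIS skin example: +26 − 18 = +8, as the SAP states.

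**Domain blank at a performed week 26 GTI, literal reading.** Interval 1 has no end value, so 0. Interval 2 has no start value, so 0. The domain contributes 0 to the year. All 27 none/mild/moderate paths were enumerated for each ordinal domain, and BMI from 24 to 36 in steps of 0.5.

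| Domain | Worsening from roll-over to week 52 | Scored | Should score | CWS error over all paths |
|---|---|---|---|---|
| Neuropsychiatric | none to moderate | 0 | +74 | −74 to 0 |
| Myopathy | none to moderate | 0 | +63 | −63 to 0 |
| Skin | none to moderate | 0 | +26 | −26 to 0 |
| BMI | 26 to 31.5 (+5.5 units) | 0 | +36 | −72 to 0 |

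The BMI extreme of −72 is a rise of at least 5 units in each interval (36 + 36). The CWS error is never above 0. The AIS error runs both ways, for example −74 to +74 for neuropsychiatric, because lost improvements count too.

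**Whole week 26 GTI missed.** Week 52 is compared with roll-over. BMI 26, 29, 29.5 scores +21 with or without week 26, so persisting toxicity is kept. The longer comparison can also score more:
- BMI 26, 27.8, 29.6: steps of 1.8 and 1.8 score 0; one step of 3.6 scores +21.
- HbA1c 5.6, 6.1, 6.6: rises of 8.9% and 8.2% score 0; one rise of 17.9% scores +32.

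**Missing medication answer.** It is treated as no change in medication and the domain is still scored. If medication had in fact decreased:
- HbA1c 5.5 to 6.3 scores +32 instead of 0.
- Systolic pressure 120 to 140 scores +19 instead of 0.
- LDL 2.5 to 3.0 scores +10 instead of 0.

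Together that is up to 32 + 19 + 10 = +61 in one interval, upward.

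**Infection.** Each interval is scored on its own. Grade 3 in both intervals gives 93 + 93 = 186; with week 26 missing it gives 93. Half is lost, not the year.

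**Comparing with the last non-missing value.** A persisting none-to-moderate neuropsychiatric worsening goes from 0 back to +74. In the ordinal domains only a transient week 26 worsening is still lost from the CWS, and the AIS error is 0. In the BMI grid the CWS error runs from −36 to +21.

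**Illustration only.** Let m be the chance that a change-scored domain is missing, independently at week 26 and week 52, with worsening that persists and is split evenly between the intervals. The literal rule loses m of the first-interval worsening and 2m − m² of the second, on average (3m − m²)/2. With the last non-missing value as comparator the average is (m² + m)/2.

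| m (assumed) | Literal rule | Last non-missing value |
|---|---|---|
| 5% | 7.4% | 2.6% |
| 10% | 14.5% | 5.5% |
| 20% | 28% | 12% |

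**The case against.** The strongest reply is that the year-long loss depends on a reading that the SAP does not spell out. Counting a missing evaluation as no change could mean that the week 26 status equals the previous one, so that week 52 is in effect compared with roll-over. That is possible. But the text assigns a weight rather than a status, and it names the previous assessment as comparator. Two programmers could therefore report different scores, which is reason enough to state the rule.

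Several stronger inferences are tempting and are not supported:

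- *That missing data can only lower the CWS.* This is true when a whole domain is set to 0. A missing medication answer, or a missed week 26 GTI, can raise it.
- *That every component is exposed.* Infection is scored per interval, hypertensive emergency/PRES regardless of the previous value, and psychosis or violence on presence. HbA1c, LDL and blood pressure are measured throughout follow-up, so the last-available-value rule largely protects them.
- *That zero-filling contradicts the complete-case statement.* SAP 4.1.3.6 defines complete cases at participant level, which is compatible with an item-level rule.
- *That pandemic home visits make this common.* Appendix 11 does not list the GTI as critical, and its nurse-measured vital signs omit weight. But it applies only in exceptional, approved cases, the GTI may move to the next on-site visit, and the week 26 analysis window is wide (day 145 to 221).

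For BMI, a large gain may also trigger the extra weighing for an obvious change. The endpoint is descriptive, with no hypothesis tested, and C-GTI data are listed individually.

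**Conclusion.** The point stands for four change-scored domains that are not measured often: BMI, myopathy, skin and neuropsychiatric effects. Under the literal rule, a blank at a performed week 26 GTI removes a persisting worsening of up to 36, 63, 26 or 74 points respectively, although the roll-over and week 52 values both exist. For these domains the effect on the CWS is downward only; the AIS can shift either way.

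This rests on the literal reading of SAP 9.1.1 and on the domain being blank while the rest of the assessment is done. The documents give no missingness rate, so the effect on the reported means cannot be computed. A reader might take the percentages above as estimates of bias; they only show how the loss grows under an assumed rate. The change is worth making because it recovers toxicity that was observed, for a stated secondary endpoint, at almost no cost.

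**What to change.** In SAP 9.1.1, state that each change-scored domain is compared with its last non-missing value, which is the roll-over value if week 26 is missing. In Table 14.2.1.8.1, add the number of participants with any domain missing at week 26 and at week 52, so that zeros that come from missing data are visible.

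The cost is a few sentences and a small programming change. Two limits remain. A transient worsening at a missing week 26 cannot be recovered. In threshold domains such as BMI, one longer comparison can score a change that two shorter ones would not, so the missing counts should be read beside the scores. A separate row for participants with all domains evaluable, or treating a domain missing at the last assessment as missing rather than 0, could be considered, but both are debatable and not needed to settle this point.
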